8.2 Study Endpoints

8.2.1 Primary Efficacy Endpoints

The primary efficacy endpoint is defined as the time from the administration of study drug to resolution of influenza symptoms and fever.

Resolution of symptoms has occurred if the following influenza symptoms (as recorded on the Flu-iiQ™) are mild in intensity or none for at least 24 hours.

- Respiratory symptoms (cough, sore throat, and nasal congestion).
- Constitutional symptoms (headache, feeling feverish, body aches and pains, and fatigue).

Resolution of fever is defined as:

- Body temperature of <37.0°C for at least 24 hours.

8.2.2 Secondary Efficacy Endpoints

- Time to resumption of normal activity as reported in Domain 2 of the Flu-iiQ™.
- Time to return to normal body temperature (<37.0°C) for at least 24 hours.
- Time to resolution of individual symptoms for at least 24 hours as recorded on the Flu-iiQ™.
- Severity of symptoms as recorded on the Flu-iiQ™.
- Viral shedding in nasopharyngeal swab samples.
- Incidence of secondary complications of influenza.
- Quality of Life (QoL) measures as reported in Domain 3 and Domain 4 of the Flu-iiQ™.

8.2.3 Secondary Safety Endpoints

The following safety parameters are secondary endpoints:

- Treatment-emergent adverse events (TEAEs)
- Treatment-emergent serious adverse events (TESAEs)
- TEAEs leading to treatment discontinuation
- Clinical laboratory analyses (hematology, biochemistry, and urinalysis laboratory tests)
- Vital sign measurements
- ECGs
- Physical examination findings

- Evaluation of ADE throughout the entire study duration. For the definition of suspicious ADE, please see [Section 6.2.5](#).

8.2.4 Exploratory Endpoints

Blood sampling for PK analysis will be collected from the subjects on:

- Day 1 at pre-infusion (within 15 minutes prior to the beginning of the infusion), the end of infusion (+15 minutes), 1 hour (± 15 minutes) after the end of the infusion,
- Day 2 (24 hours [± 4 hours] after the start of the study drug infusion),
- Day 3 (48 hours [± 4 hours] after the start of the study drug infusion),
- Day 8 (168 hours [± 4 hours] after the start of the study drug infusion),
- Day 15 (± 2 days), Days 29, 57 and 110 (± 5 days) or at end of study visit (EOS visit).

Blood sampling for Immunogenicity assessment will be collected on Day 1 (at pre-infusion) and Day 110 (± 5 days) or EOS visit.

For the subjects with Influenza A confirmed by qPCR or cell culture, genotypic analysis on HA and NA genes, and phenotype characterization of potential escape variants with regard to CT-P27 will be evaluated using the nasopharyngeal swab samples.

Blood sampling for assessment of anti-influenza antibodies (Hemagglutination inhibition) will be collected on Day 1 (at pre-infusion) and Day 29 (± 5 days) or EOS visit (if a subject is early terminated from the study) in Subgroup (PK) Cohort.

Additional genotyping tests could be conducted if it is required from a regulatory or medical perspective.

The following parameters are determined as exploratory endpoints:

- PK profiles
 - $AUC_{0-\infty}$: Area under the concentration-time curve in serum from time zero extrapolated to infinite time
 - AUC_{0-last} : Area under the concentration-time curve from time zero to the last quantifiable concentration
 - C_{max} : Maximum observed serum concentration
 - t_{max} : Time of maximum concentration
 - C_{last} : Last observed quantifiable concentration
 - λ_z : Apparent terminal elimination rate constant

- $t_{1/2}$: Apparent terminal elimination half-life
 - MRT: Mean residence time
 - CL: Systemic clearance from serum after IV dosing
 - V_z : Apparent volume of distribution during the terminal elimination phase after IV dosing
- Anti-drug specific antibodies for CT-P27 component antibodies (CT-P22 and CT-P23)
 - HI antibody.
 - Genotype and phenotype of isolated influenza virus

8.3 Statistical Methods

The statistical analysis will be performed using [REDACTED]. The statistical methods for this study, summarized in the following, will be described in a detailed SAP, which will be finalized prior to locking of the database and unblinding of the treatment codes. Changes from analyses planned in this protocol will be documented in the SAP. Any deviations from the planned analysis as described in the SAP will be justified and recorded in the final study report.

The data documented and the clinical parameters measured in this study will be described using descriptive statistics (including number [n], mean, median, SD, minimum, and maximum) for quantitative variables and frequency counts and percentages for qualitative variables. Data will be listed in data listings.

Baseline will be the latest available measurement prior to the start of the infusion of study drug.

Pharmacokinetic parameters will be computed by non-compartmental methods [REDACTED].

8.4 Analysis Populations

8.4.1 Intent-to-Treat Population

The intent-to-treat (ITT) population is defined as all subjects randomized to study drug or placebo. All subjects will be included in the ITT as randomized even if they do not receive treatment. The secondary efficacy endpoint analysis and all baseline and demographic summaries will be performed on the ITT population.

8.4.2 Intent-to-Treat Infected Population

The intent-to-treat infected (ITTI) population is defined as all randomized subjects with confirmed influenza A by qPCR or cell culture. The primary and secondary efficacy endpoint analysis, the genotype and phenotype analysis will all be performed on the ITTI population.

8.4.3 Safety Population

The safety population is defined as all randomized subjects receiving any amount of placebo or CT-P27. All safety and immunogenicity analyses will be based on the safety population.

8.4.4 Pharmacokinetic Population

The PK population is defined as approximately 53 subjects (20 per CT-P27 treatment groups and 13 in placebo group) in Subgroup (PK) Cohort and all randomized subjects with confirmed influenza A by qPCR or cell culture who received a complete dose of study drug, with at least one post-dose PK sample. All PK analyses will be based on the PK population.

If infusion interruptions and/or infusion rate adjustments occur during drug administration, the subject is still considered to have received a complete dose provided that the full calculated dose (45 mg/kg or 90 mg/kg) has been given at the end of the infusion. The infusion duration will be longer than 90 minutes (± 15 minutes) in these cases and this will be documented in the eCRF.

In addition, HI antibody, and the subject baseline characteristics analysis will all be performed on the PK population.

8.5 Statistical Analyses

8.5.1 Primary Efficacy Analysis

The primary efficacy endpoint analysis will assess the time (in days) from the administration of study drug to resolution of influenza symptoms and fever. This analysis will be performed on the ITTI population. Data will be obtained from responses recorded on the Flu-iiQ™.

Resolution of symptoms has occurred if the following influenza symptoms (as recorded on the Flu-iiQ™) are mild in intensity or none for at least 24 hours.

- Respiratory symptoms (cough, sore throat, and nasal congestion).
- Constitutional symptoms (headache, feeling feverish, body aches and pains, and fatigue).

Resolution of fever is defined as:

- Body temperature of $<37.0^{\circ}\text{C}$ for at least 24 hours. (The start time for resolution of fever is defined as the time recorded in the diary when body temperature was $<37.0^{\circ}\text{C}$ for at least 24 hours.)

If the subject has received the drugs for symptom relief, the effective duration of the drugs for symptom relief should be considered.

For example, the study drug was administered at 12:00 on 1st day. The first time body temperature recorded $<37.0^{\circ}\text{C}$ in the diary was 10:00 on 2nd day and continued more than 24 hours. But acetaminophen/paracetamol known to be effective for 6 hours had been administered at 09:00 on 2nd day [1 hour prior to the time when the body temperature decreased $<37.0^{\circ}\text{C}$], it will be calculated that the start time point for body temperature $<37.0^{\circ}\text{C}$ is 15:00 on 2nd day [27 hours after the study drug administration]. Then, if the next first time body temperature recorded $<37.0^{\circ}\text{C}$ in the diary was 22:00 on 2nd day and body temperature was $<37.0^{\circ}\text{C}$ for 24 hours from then, the start time for resolution of fever is 22:00 on 2nd day [34 hours after the study drug administration].

The primary efficacy endpoint will be analyzed using a Wilcoxon rank-sum test to assess differences between treatment groups, if every subject were followed until resolution of influenza symptoms and fever. The statistically significant difference of time to resolution of influenza symptoms and fever between placebo and CT-P27 based on Wilcoxon rank-sum test will be presented by p-values. If there is any censoring, the primary efficacy endpoint will be analyzed using Log-rank test, and Kaplan-Meier plots will be presented.

8.5.2 Secondary Efficacy Analyses

The secondary efficacy endpoints will be analyzed on the ITTI and ITT populations.

Time (in days) to resumption of normal activity, return to normal body temperature ($<37.0^{\circ}\text{C}$), and resolution of individual symptoms will be analyzed using a Kaplan Meier model to assess differences between placebo and CT-P27.

Individual symptoms and total symptom score will be summarized by severity, by time point, and by treatment group.

Viral shedding (titers) based on qPCR and cell culture will be evaluated at the scheduled collection times. Changes in viral shedding will be assessed as the change from baseline in qPCR and \log_{10} TCID₅₀/mL.

These will be summarized for each treatment group and collection time.

The number and percentage of subjects with secondary complications of influenza will be summarized by treatment group.

Results for questions included in the remaining domains (3 and 4) (effect on feelings, effect on concerns) of the Flu-iiQ™ will be summarized by collection time and treatment group.

Scheduled selection times are presented in [Table 1](#).

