5.3 Analysis Populations

ITT and ITTI populations will be analyzed according to the randomized treatment groups and safety and PK populations will be analyzed according to the actual treatment groups.

- Intent-to-Treat (ITT) Population: defined as all subjects randomized to study drug. All subjects will be included in the ITT as randomized even if they do not receive treatment, except

Statistical Analysis Plan

for the following situation:

Subjects who are screening failures but are randomized in the IWRS by accident and do not receive any study drug will not be included in the ITT population.

- Intent-to-Treat Infected (ITTI) Population: defined as all randomized subjects with confirmed influenza A by quantitative Polymerase Chain Reaction (qPCR) or cell culture.
- Safety Population: defined as all randomized subjects receiving any amount (full or partial dose) of study drug, except for the following situation:
Subjects who do not receive study drug but receive normal saline solution will be included in the safety population and they will be analyzed in the placebo group.
- PK Population: defined as all randomized subjects with confirmed influenza A by qPCR or cell culture who received a complete dose of study drug, with at least one post-dose PK sample.

If infusion interruptions and/or infusion rate adjustments occur during the drug administration, the subject is still considered to have received a complete dose provided that the full calculated dose (45 mg/kg or 90 mg/kg) has been given at the end of the infusion.

The analysis populations will be used for the analyses as follows:

- ITT Population:
 - Demographic and baseline characteristics
 - Use of drugs for symptom relief
 - Secondary efficacy endpoints
- ITTI Population:
 - Demographic and baseline characteristics
 - Primary efficacy endpoint
 - Secondary efficacy endpoints
 - Genotype
 - Phenotype
- Safety Population:
 - Viral serology
 - Prior and concomitant medications
 - Study drug exposure
 - Safety endpoints
 - Immunogenicity
- PK Population:
 - Demographic and baseline characteristics
 - PK analysis
 - HI antibody

HI antibody, genotype and phenotype will be analyzed in the Follow-Up CSR only.

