8.2 Clinical Characteristics

The following continuous variables will be summarized using descriptive statistics by treatment group:

- Duration from onset of illness to study drug administration (hours): [Start date/time of study drug administration] – [Date/time of onset of illness]
- Influenza symptoms score at screening: Average scores of respiratory, constitutional, systemic and total symptoms
- Body temperature (°C) at screening

The following categorical variables will be summarized in contingency tables:

- Influenza subtype (Influenza A/H1, Influenza A/H3, Influenza A/H1 and H3, Unknown, NA)
- Influenza confirmed (by cell culture, qPCR, both, no)
- Rapid kit test results (positive, negative)

When influenza A virus load from qPCR has quantitative value or less than Lower Limit of Quantification (LLOQ), then influenza is confirmed. However, when influenza A virus load from cell culture has only quantitative value, then influenza is confirmed by cell culture.

Summary tables will be presented for ITT, ITTI, and PK populations. Also data will be listed for the ITT population.

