Viral shedding (titers) of swab samples based on qPCR and cell culture will be evaluated at the scheduled collection times. The listing will include titer results, whether the influenza A is confirmed and Area under the Curve (AUC) of viral loads. However, since cell culture results have information of both influenza A and B, the listing and tables for cell culture will present analysis results regardless of influenza type. Changes in viral shedding will be assessed as the change from baseline in \log_{10} vp/mL and \log_{10} TCID₅₀/mL for qPCR and cell culture respectively. If viral loads are lower than LLoQ (2.18 for qPCR), they will be treated as value without inequality sign. Whereas viral load lower than LLoQ for cell culture (0.75) will be considered as negative value and a negative value will be treated as 0. If the subtype of influenza A is "H1", "NA" or "Unknown", the virus titer from HA assay will be used for cell culture analysis. Otherwise, if the subtype is "H3", the virus titer from NP ELISA will be used.

These will be summarized for each treatment group and collection time.

The following analyses will also be performed:

- Summary of viral shedding results; percentage of subjects with positive/negative viral shedding at each visit (baseline, day 2, 3, 5, 8)
- Duration (in days) of viral shedding; from date/time of baseline assessment to last positive sample. Subjects with at least one positive sample after baseline will be included in the summary.

Statistical Analysis Plan

- AUC of viral levels; from date of baseline assessment to last measurable value of subjects who have at least one post-baseline result (including BLQ (Below the Limit of Quantification) and negative values). If there are BLQ or missing values between measurable values, they are assumed to fall linearly between measurable values.
- Change from baseline in descriptive statistics of viral shedding of Swab Samples; descriptive statistics of actual value and change from baseline for viral shedding of swab samples will be presented by treatment group at each visit.
- Mean viral load titer (log values)
Mean viral load titer for each scheduled time point will be plotted with the SD of mean value.

- Incidence of secondary complications of influenza

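### Cell-culture change from baseline averages in ITTI subjects whose baseline culture titer is already 0, so the described antiviral difference is diluted

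*Protocol*

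**What the plan says.** - Protocol 8.5.2 on populations: "The secondary efficacy endpoints will be analyzed on the ITTI and ITT populations". On titer: "Changes in viral shedding will be assessed as the change from baseline in qPCR", and in log10 TCID50/mL for culture.
- SAP 10.2 carries this out: "descriptive statistics of actual value and change from baseline for viral shedding of swab samples will be presented by treatment group at each visit". The table list has one change table per assay and population: 14.2.13.1.1 and 14.2.13.1.2 for qPCR, 14.2.13.2.1 and 14.2.13.2.2 for culture (ITT and ITTI respectively). Figures with the same numbers plot mean titer rather than change.
- ITTI is "all randomized subjects with confirmed influenza A by qPCR or cell culture" (Protocol 8.4.2; SAP 5.3 has the same rule). Positivity by the assay being tabulated is not required, and the rule does not say that the confirming sample is the baseline one.
- SAP 8.2 foresees confirmation by one assay alone, since its categories read "Influenza confirmed (by cell culture, qPCR, both, no".
- SAP 10.2 on culture: "viral load lower than LLoQ for cell culture (0.75) will be considered as negative value and a negative value will be treated as 0". For qPCR, a result below the LLoQ is kept at 2.18, and SAP 8.2 counts it as confirmed infection.
- Duration of shedding is limited to subjects with a positive sample after baseline. Change from baseline has no positivity condition. The percentage positive and negative is tabulated at baseline and at each later swab.

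**The concern.** A subject whose baseline culture is set to 0 cannot show a fall in culture titer, whatever the treatment does. Such subjects say nothing about the speed of viral decline, yet they count fully in each arm's mean change and mean titer. The gap between CT-P27 and placebo then looks smaller than it is among subjects who had culturable virus to clear.

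This matters because the study is set up to obtain effect sizes, and Protocol 6.5 treats the quantitative change in shedding as its leading virology outcome. An attenuated difference could be carried forward as the antiviral effect size.

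**Working it through.** **The plan's own figure.** The documents state no effect size, SD or power for viral titer, so there is nothing to reproduce. The sample-size section concerns the primary endpoint; only its group sizes (63 per dose, 38 placebo) are used here.

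**Step 1: who is affected.** Take an ITTI subject who is qPCR-positive and has a baseline culture below 0.75.
- Baseline culture value = 0.
- Change at a later visit = later value - 0, which is 0 or more.

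No table or text in SAP 10.2 removes this subject from the culture change summary. The inclusion follows from the lack of any restriction; no sentence states it outright.

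**Step 2: size of the dilution.** Let f be the share negative by culture at baseline (similar in each arm, since it is fixed before dosing), and d the between-arm difference in mean fall among baseline-positives.
- If baseline-negatives stay at 0: tabulated difference = (1 - f) x d.
- If they rise later by means r0 (placebo) and r1 (active): tabulated difference = (1 - f) x d + f x (r0 - r1).

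The first line is the simple case used below. For the spread, with mean fall m and SD s among baseline-positives, the variance over all subjects is (1 - f)(s² + f m²).

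The documents do not give f, d, m or s. The values d = 0.8, m = 2 and s = 1.5 log10 are assumptions for illustration; the column (1 - f) does not depend on them.

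| f | (1 - f) | Difference (d = 0.8) | SD | Difference / SD |
|---|---|---|---|---|
| 0% | 1.00 | 0.80 | 1.50 | 0.53 |
| 10% | 0.90 | 0.72 | √2.385 = 1.54 | 0.47 |
| 20% | 0.80 | 0.64 | √2.440 = 1.56 | 0.41 |
| 30% | 0.70 | 0.56 | √2.415 = 1.55 | 0.36 |
| 40% | 0.60 | 0.48 | √2.310 = 1.52 | 0.32 |

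The loss comes almost entirely from the smaller difference. The SD rises by about 4% at most, and exceeds s only when f < 1 - s²/m² = 1 - 2.25/4 = 44%.

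**Step 3: qPCR.** A detected result below the LLoQ enters at 2.18, not 0, and still counts as infected. To be a qPCR-negative at baseline within ITTI, a subject must have no qPCR detection then and be confirmed by culture or on a later sample. Such subjects should be few. Whether an undetected qPCR result is itself valued at 0 is unclear, because the zero rule sits in the sentence on culture.

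**Step 4: ITT.** The planning assumption of 90% infected implies about 10% of ITT unconfirmed, a factor of about 0.90 in either assay (for qPCR, if undetected is read as 0). This adds to whatever f is in ITTI.

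**The case against.** The strongest reply is that nothing here is wrong as an estimand. The mean change in all infected, or all randomised, subjects is a legitimate randomised quantity, and it is what the Protocol prespecifies. The effect among baseline-positives is a different target. The share f will be visible in the percent-positive table, actual values accompany the changes, medians are standard, and individual titers are listed.

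Much of this stands. It is why the all-subject summaries should remain. It does not remove the point: the percent-positive table shows f, but a reader cannot recover the baseline-positive mean and SD by arm from it exactly, because baseline-negatives may turn positive later.

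A reader might also infer more than the documents support:
- **That the analysis loses power.** Under the Step 2 assumptions, a two-sided 5% comparison of 63 with 38 would have 62/51/42/34% power on all subjects and 69/64/58/52% on baseline-positives at f = 10/20/30/40%. No such test is planned, so these figures are illustrative only.
- **That restriction always gains precision.** This needs baseline-negatives to stay at 0. If treatment prevents later rises, that is a real effect, and a restricted table misses it.
- **That both assays are affected alike.** Within ITTI this is essentially a culture problem (Step 3).
- **That ITT dilution is a fault.** It is inherent to ITT, and the parallel ITTI tables already answer it.
- **That dose selection is misled.** SAP 1.1 ties dose selection to effect size on time to resolution, plus safety and PK; Protocol 2.2 adds efficacy only in general terms. Neither names viral titer.

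**Conclusion.** The point holds for the cell-culture change summaries and the matching mean-titer figures in ITTI. Subjects confirmed by qPCR only enter at 0 and cannot show a decline, so the described between-arm difference shrinks by about (1 - f). With f assumed between 10% and 40%, 90% to 60% of the difference remains. This rests on three things: baseline-negatives stay at or near 0, f is similar across arms, and the missing restriction is read as inclusion. The effect on the SD is minor, and type I error is not at issue. It is a cheap improvement to a descriptive secondary read-out, not a flaw in the trial's main comparison.

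**What to change.** In SAP 10.2 and the table and figure list:

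- Add change-from-baseline tables and mean-titer figures in ITTI subjects positive by that assay at the pre-dose sample (culture at or above 0.75 log10 TCID50/mL; qPCR detected). Name these as the main read-out of antiviral effect size. Positivity is measured before dosing, so the randomised comparison is kept.
- Show the number excluded in each arm.
- Keep the all-ITTI and ITT change summaries that Protocol 8.5.2 requires, and the percent-positive-by-visit table on all subjects.
- List baseline-negative subjects who later turn positive.
- State the numeric value given to an undetected qPCR result.

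The cost is a few lines in the SAP and a filter in the programs. The added culture tables will be smaller: at f = 10%, 63 and 38 become about 57 and 34 (63 x 0.9 and 38 x 0.9); at f = 40%, about 38 and 23 (63 x 0.6 and 38 x 0.6). They also do not capture later rises in baseline-negative subjects, which is why the listing and the all-subject tables stay.
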